Summary tables for PK concentration and IM data will be presented by Treatment naive group, CS6-Volanesorsen, CS16-Volanesorsen, and Volanesorsen combined (i.e., CS6-Volanesorsen and CS16-Volanesorsen combined). Summary figures for PK concentration data and summary tables for PK parameters will be presented by Treatment naive group and Volanesorsen combined.

Total patient year of exposure will be calculated as summation of [minimum (latest visit date, data cutoff date) – treatment start date +1]/365.25 for all subjects.

For listings, data will be displayed as an order of following:

- Treatment naive group: CS7-New
- Treatment naive group: CS6-Placebo
- Treatment naive group: CS16-Placebo
- CS6-Volanesorsen
- CS16-Volanesorsen

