3.2.4 Patient Baseline data, Medical history and Disposition

Summary tables in this section will be presented for the FAS by the group presented in [Section 3.2.1](#).

Baseline data (demographic, disease history and baseline disease characteristics) will be summarized. It will also be displayed in the patient data listings.

- Demographic including age, gender, ethnicity, race, weight and BMI will be summarized using descriptive statistics by the group presented in [Section 3.2.1](#). Age is calculated by using the informed consent date of the open-label study and birth date. Gender, ethnicity and race for Group 1 and 2 patients were collected in each index study.
- Disease history includes duration of FCS diagnosis at screening, age at FCS diagnosis, lipemia retinalis, eruptive xanthomas history, pancreatitis history, glybera treatment history, confirmation for known loss-of-function mutations in Type 1-causing genes, documentation of post heparin plasma LPL activity <=20% of normal based on medical history, confirmation for type 1 phenotype based on genetic sequencing results, post heparin plasma LPL activity <=20% of normal based on lab results, , and history of type II diabetes.

- Baseline disease characteristics includes: body weight, height at Day 1 of the Open-label study, Body Mass Index (BMI) , fasting lipids results including TG, LDL-C, HDL-C, Total Cholesterol, non-HDL-C, VLDL-C, apoA-1, apoB and apoC-III.

Medical history collected in the open-label study will be coded by Medical Dictionary for Regulatory Activities (MedDRATM) dictionary version 19.1 and will be summarized by system organ class and preferred term for the Safety Set. Medical history will also be provided in the patient data listings.

Patient disposition of the open-label study will be summarized for all enrolled patients. The number of patients enrolled, dosed, completed treatment, along with reasons for discontinuing treatment and withdrawing from the study, completed post-treatment follow-up, along with reasons for early terminating post-treatment follow-up, will be presented. Patient disposition through CS6 and CS7 will also be summarized.

Treatment discontinuation by month will be presented through index studies and open-label study to present number of patients discontinued in each study month and corresponding discontinuation reason, and remaining number of patients in the study.

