Summary of discontinuation rate per patient year of exposure in the index studies and open-label study overall will be generated.

Kaplan Meier Plot of Treatment Continuation will be provided for below comparisons:

- CS6 volanesorsen arm vs CS7 treatment naive group in patients with history of pancreatitis
- CS6 volanesorsen arm vs CS7 treatment naive group in patients with history of pancreatitis through Month 12
- CS6 volanesorsen arm vs CS7 treatment naive group in safety set through Month 12

Listing of patient disposition will also be provided.

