3.3.9 Adjudicated acute pancreatitis events Rate

Yearly rate of adjudicated acute pancreatitis events and patient reported moderate or severe abdominal pain (pain score: 4-10) for FAS during the on-treatment period of the Open-label study, calculated as $365.25 \times \text{the number of events during the on-treatment period} / \text{on-treatment duration}$, will be summarized with descriptive statistics. At each mapped visit window of abdominal pain, at most one moderate or severe event will be counted to calculate the yearly rate. Adjudicated acute pancreatitis event rate prior to first dose of Study Drug (including events based on medical chart review) vs. treatment emergent events will be summarized.

Yearly rate of adjudicated acute pancreatitis events and patient reported moderate or severe abdominal pain (pain score: 4-10) for patients who administered volanesorsen in Index studies will be calculated and summarized, including events occurred during either index study or open-label study.

On-study and on-treatment pancreatitis incidence rate per patient year of exposure will be summarized.

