3.4.2 Immunogenicity (IM) Analysis

Immunogenicity (IM) analyses will be conducted in Safety Set.

Samples collected for IM assessment at selected time points will be analyzed for anti-volanesorsen antibodies (i.e., anti-drug antibodies; ADA). Samples will be designated 'IM positive' based on both positive screening and confirmation assay results (i.e., confirmed positive result), and otherwise be deemed 'IM negative'. Study subjects will be given 'positive' subject IM status if they have at least one confirmed positive sample at any time during the treatment or post-treatment evaluation periods. Study subjects will be given 'negative' subject IM status if all evaluated IM sample results during the treatment and post-treatment evaluation periods are negative and they have at least one evaluable IM result post dose. Otherwise, study subjects will be given 'unknown' subject IM status.

Sample IM status (screen positive/negative, confirmed positive/negative or not evaluable, and when applicable, titer of anti-volanesorsen antibodies) before, during, and after treatment with Study Drug (volanesorsen or placebo) will be listed for Group 1 and Group 2 patients by their prior treatment in Study ISIS 304801-CS6 and ISIS 304801-CS16 and newly enrolled patients as a separate group (Group 3) by study day. Subject IM status (positive/negative or unknown) for all evaluable patients, along with the study day associated with the first positive IM status emerged (T_{first} , i.e., onset of ADA development), the last positive IM status observed (T_{last}) and max and/or end of treatment titer will be listed by treatment and dose.

Additionally, the sample and patient IM incidence (number) and incidence rate (percent) will be summarized as the total number and percent of evaluated patients with antibody negative, positive, and unknown status by the group presented in [Section 3.2.1](#). Furthermore, onset, and peak titer of the ADA response, if applicable, will be summarized as median, interquartile range (25th percentile, 75th percentile), and range (minimum, maximum).

Potential relationships between immunogenicity results (e.g., IM status) and selected efficacy (e.g., % change in fasting TG from baseline at 3-, 6-, and 12-month endpoints), safety, and pharmacokinetic measures will be evaluated in an exploratory manner.

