3.5 Safety Analyses

Safety endpoints including treatment exposure, AEs, clinical safety lab, vital signs, physical examination, 12-lead ECG, Echocardiogram, prior and concomitant medication use, and MRIs will be summarized in Safety Set.

On-Study period (from **Day 1 of Volanesorsen** to end of the study) in the open-label study will be classified to 3 periods:

- On-treatment period: from the first dose of Volanesorsen to the last dose of Volanesorsen + 28 days
- After-treatment period: from the last dose of Study Drug + 29 days to the last dose of study medication + 90 days
- Post-follow up period: after the last dose of Study Drug + 90 days

For vital sign, clinical safety lab, or 12-lead ECG,

- Visits of summary tables include baseline and labeled post baseline visits in the open-label study.
- **Safety Baseline** is defined in the [section 3.2.3](#) of this SAP.

For AEs, prior and concomitant medication use, each summary table will present the open-label study data.

For treatment exposure, details are discussed in the [section 3.5.5](#) of this SAP.

By patient data listings will display data collected in the open-label study.

In this section, **Day 1 of Volanesorsen** is defined as the first day volanesorsen is administered to the patient. For patients on active treatment in the index study, Day 1 of Volanesorsen will be the first day volanesorsen is administered in the index study. For patients on placebo in the index study, Day 1 of Volanesorsen will be the first day volanesorsen is administered in this open-label study.

Patient profile figures will be generated for selected patients to provide graphical profile of endpoint of interest.

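### Patient-years of exposure run to the latest visit or cutoff, so the on-treatment pancreatitis incidence rate and the discontinuation rate come out too low

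*SAP*

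**What the plan says.** SAP Section 3.2.1 holds the plan's only patient-year formula: "Total patient year of exposure will be calculated as summation of [minimum (latest visit date, data cutoff date"), minus the treatment start date, plus 1, divided by 365.25 and summed over all subjects. It does not say whether the start is that of the index study or of the open-label study.

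The term is then used for these rates:

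- Section 3.3.9: "On-study and on-treatment pancreatitis incidence rate per patient year of exposure will be summarized".
- Section 3.2.4: "Summary of discontinuation rate per patient year of exposure in the index studies and open-label study overall will be generated".

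Section 3.5 limits the events that count as on-treatment: "On-treatment period: from the first dose of Volanesorsen to the last dose of Volanesorsen + 28 days".

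Section 3.3.9 also plans a separate yearly rate of pancreatitis and of "moderate or severe abdominal pain (pain score: 4-10) for FAS during the on-treatment period of the Open-label study". That rate divides by on-treatment duration.

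Follow-up off drug is planned. Section 2.1.2 asks for at least 12 weeks of platelet monitoring after early stopping and encourages landmark visits up to Week 52. Section 2.1.5 gives a 13-week post-treatment period to patients who do not enter expanded access.

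**The concern.** A rate is interpretable only if its denominator is the time during which its events could be counted. The Section 3.2.1 formula meets that test for the on-study pancreatitis rate but not for the other two.

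- **On-treatment pancreatitis incidence.** Events later than 28 days after the last dose are excluded, but the days on which they would have fallen still count.
- **Discontinuation.** A patient who has stopped or completed dosing cannot discontinue treatment again, but every later day up to the last visit still counts.

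Both errors lower the rate, one flattering benefit and the other tolerability. Section 3.3.9 would also report two on-treatment pancreatitis rates on different time bases without saying so.

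**Working it through.** The SAP states no rate or patient-year total, so there is no figure to reproduce. The check is person-time arithmetic.

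**Inputs.** Study days follow (week − 1) × 7 + 1: Week 13 = 85, Week 26 = 176, Week 52 = 358, Week 65 = 449, Week 104 = 722, Week 117 = 813 (Sections 3.2.1 and 3.4.1). The on-treatment tail is 28 days (Section 3.5). Planned off-drug follow-up is 12 weeks = 84 days after early stopping (Section 2.1.2) or 13 weeks = 91 days (Section 2.1.5).

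**Single patients.** With last dose on day s and latest visit on day f:

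- on-treatment shortfall = 1 − min(s + 28, f)/f
- discontinuation shortfall = 1 − s/f

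| Patient | s | f | On-treatment shortfall | Discontinuation shortfall |
|---|---|---|---|---|
| Week 52 completer, seen at Week 65 | 358 | 449 | 1 − 386/449 = 14% | 1 − 358/449 = 20% |
| Week 104 completer, seen at Week 117 | 722 | 813 | 1 − 750/813 = 8% | 1 − 722/813 = 11% |
| Stops Day 85, 12 weeks of monitoring | 85 | 169 | 1 − 113/169 = 33% | 1 − 85/169 = 50% |
| Stops Day 85, attends the optional Week 52 visit | 85 | 358 | 1 − 113/358 = 68% | 1 − 85/358 = 76% |
| Last seen 21 days after last dose | 358 | 379 | 0 | 1 − 358/379 = 6% |
| Last seen on day of last dose | 358 | 358 | 0 | 0 |

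**Cohort, under assumptions.** The SAP gives no discontinuation, extension or expanded-access figures. I assume:

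- a share p = 0.1–0.4 stops at s = 85 or 176 and is followed to f = s + 28, s + 84 or 358;
- completers have last dose L = 358 (none extended) or 722 (all extended);
- a share e = 0–1 of completers is last seen at L (leaving for expanded access), the rest at L + 91.

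Then:

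- time as written: D = p·f + (1 − p)[L·e + (L + 91)(1 − e)]
- on-treatment time: T = p(s + 28) + (1 − p)[L·e + (L + 28)(1 − e)]
- time at risk of discontinuing: R = p·s + (1 − p)L

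The shortfalls are 1 − T/D and 1 − R/D.

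*Largest* (p = 0.4, s = 85, f = 358, e = 0):

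- L = 358: D = 412.6, T = 276.8, R = 248.8, giving 32.9% and 39.7%.
- L = 722: D = 631.0, T = 495.2, R = 467.2, giving 21.5% and 26.0%.

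*Smallest* (p = 0.1, s = 176, f = 204, e = 1): 0% on-treatment; discontinuation 1 − 339.8/342.6 = 0.8% (L = 358) and 1 − 667.4/670.2 = 0.4% (L = 722).

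*Stoppers followed for the planned 12 weeks only* (f = s + 84): on-treatment 2–18% (L = 358) and 1–11% (L = 722). The upper ends for discontinuation are 1 − 248.8/337.0 = 26% and 1 − 467.2/555.4 = 16%.

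**Adding index volanesorsen time.** Section 3.4.1.2 gives 12 months for CS6 and 6 for CS16. Taking these as A = 364 and 182 days with no gap, and adding A to R and D, the discontinuation maxima (L = 358; L = 722) become:

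- CS16: 1 − 430.8/594.6 = 27.5%; 1 − 649.2/813.0 = 20.2%
- CS6: 1 − 612.8/776.6 = 21.1%; 1 − 831.2/995.0 = 16.5%

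Adding A = 364 to the on-treatment rate as well lowers its maxima to 1 − 640.8/776.6 = 17.5% and 1 − 859.2/995.0 = 13.6%.

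**The case against.** **The link to the formula is inferred.** Neither rate cites Section 3.2.1, and a programmer might restrict time to match the events, as the yearly rate in Section 3.3.9 does. But the term is defined once, the rates use it by name, and the summary of changes describes both the formula and the pancreatitis rate as coming from ad hoc analyses. A defined term is normally programmed as defined.

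**Discontinuation might mean leaving the study,** for which time to latest visit is suitable. Section 3.2.4 does not settle this outright. However, the preceding paragraph reads "Treatment discontinuation by month will be presented through index studies and open-label study", and the plots that follow show continuation of treatment, so stopping drug is the natural reading.

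**The direction has exceptions.** The zero on-treatment effect for patients last seen within 28 days of the last dose relies on capping their time at the latest visit, which Section 3.5 does not state. Without the cap such a patient pulls the other way (386/358 = 1.078). In a mix of 10% Week 65 completers, 10% Day 176 stoppers seen to Day 358 and 80% with no off-drug follow-up, the on-treatment effect nets to about nil. A dose taken after the last recorded visit would also pull that way. These edge cases stand, but time in which nobody is observed does not belong in an incidence denominator.

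**The cohort range is wide and rests on assumptions.** This stands. The grid omits patients who stopped during an index study and stopping during the extension. The 68% and 76% examples need a visit that is only encouraged.

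**Much is already covered.** The matched yearly pancreatitis rate, discontinuation by month and Kaplan-Meier plots are all planned. That limits the severity but does not make the two rates right.

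**Conclusion.** The concern holds, as a minor point. Applied as written, the definition understates the on-treatment pancreatitis incidence rate wherever patients are followed more than 28 days off drug, and the discontinuation rate wherever any off-drug time is counted. The on-study incidence rate and the yearly rate based on on-treatment duration are not affected.

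For patients who follow the planned schedule, the shortfall is 8–33% on-treatment and 11–50% for discontinuation (first three rows of the table). Across the assumed cohorts it is 0–33% and 0.4–40%, the upper ends applying to patients without index volanesorsen time. The true figure depends on disposition and on whether a platelet draw counts as the latest visit, neither of which the SAP gives. These conclusions take discontinuation to mean stopping treatment and cap on-treatment time at the latest visit. All analyses are descriptive, and no study conclusion rests on these two rates alone.

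**What to change.** State the person-time for each rate:

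- **On-study rates:** keep the present formula.
- **On-treatment incidence rates:** [min(last volanesorsen dose + 28 days, latest visit, cutoff) − start + 1]/365.25.
- **Discontinuation rate:** time on treatment, from start to the earlier of last dose and cutoff; say that treatment discontinuation is meant.
- **Start date:** Day 1 of Volanesorsen (Section 3.5) when index and open-label periods are combined; the first open-label dose when only open-label events are counted.
- **Index placebo time:** keep it out of volanesorsen person-time. Section 3.5 already does this for Day 1: for patients "on placebo in the index study, Day 1 of Volanesorsen will be the first day volanesorsen is administered in this open-label study". Section 3.5.5 duration should not be reused unchanged for the combined period, because it is built on Study Drug, and Section 3.4.2 speaks of "treatment with Study Drug (volanesorsen or placebo"). For open-label time alone this does not matter, since all dosing is volanesorsen.

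The cost is a few lines of wording and one extra derived variable, with no new data. The two rates become less favourable wherever patients were followed off drug.

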3.2.2 Patient Population Analyzed

The following analysis populations will be used for the analysis of data as described within each analysis set.

Full Analysis Set (FAS): All patients who are enrolled and received at least one dose of Study Drug and who have an open-label study baseline TG assessment. The FAS represents the practically-feasible intent-to-treat (ITT) population as delineated in ICH Guideline E9.

The significant deviation criteria are listed in Appendix A.

All protocol deviations will be listed in the patient data listings.

Safety Set: All patients who are enrolled and receive at least one dose of Study Drug. Group 1 and Group 2 patients will be summarized in the actual treatment group patients received during index study. Patients randomized to receive placebo in the index study, incorrectly treated with volanesorsen during the index study treatment period will be counted in the volanesorsen group from the first dose of volanesorsen received.

PK Population: All patients who are enrolled and receive at least one dose of Study Drug, and have at least one post first dose PK sample collected, analyzed, and not excluded by PK scientist as the PK result was considered to be an outlier. Group 1 and Group 2 patients will be summarized in the actual treatment group patients received during index study. Patients randomized to receive placebo in the index study, incorrectly treated with volanesorsen during the index study treatment period will be counted in the volanesorsen group from the first dose of volanesorsen received. Group 3 patients will be summarized under Treatment naive group.

All efficacy endpoints will be assessed in the FAS. All safety assessments will be performed on the Safety Set. PK endpoints will be assessed in the PK Set as applicable.

Analysis populations will be summarized with counts and percentages by the group presented in [Section 3.2.1](#).

3.2.3 Baselines and Other Definition

Baselines for fasting lipid measurement:

Definitions of baselines, including the **Index Study Baseline** (for Group 1 and Group 2 only) and the **Open-label Study Baseline** (for Group 1, 2, and 3), are given below for the purposes of the final analysis.

- **Index Study Baseline for Group 1 and 2** is defined as the average of Index Study Day 1 pre-dose assessment and the last measurement prior to Index Study Day 1 pre-dose assessment. If one of the two measurements is missing, then the other measurement will be assigned as the baseline value. If both are missing, then the baseline will be set as missing.
- **Open-label Study Baseline for Group 1, 2 and 3** is defined as the average of open-label Day 1 pre-dose assessment and the last measurement prior to open-label Day 1. If one of the two measurements is missing, then the other measurement will be assigned as the baseline value. If both are missing, then the baseline will be set as missing.

Baselines for QOL (EQ-5D, SF-36):

1. **Index Study Baseline for Group 1** is defined as the last non-missing assessment on Week 1 of treatment, volanesorsen or Placebo, in index studies.
2. **Open-label Study Baseline for Group 1, 2 and 3** is defined as the last non-missing assessment on Week 1 in this Open-label study.

Baselines for patient reported abdominal pain:

1. The average of maximum intensity:
2. **Index Study Baseline for Group 1** is defined as the average of maximum intensity during the screening period and Week 1 in index studies.
3. **Open-label Study Baseline for Group 1, 2 and 3** is defined as the average of maximum intensity within 4 weeks (including week 1) prior to Day 1 of treatment in this open-label study.
4. The worst of maximum intensity:
5. **Index Study Baseline for Group 1** is defined as the worst of maximum intensity during the screening period and Week 1 in index studies.
6. **Open-label Study Baseline for Group 1, 2 and 3** is defined as the worst of maximum intensity within 4 weeks (including week 1) prior to Day 1 of treatment in this open-label study.

Safety Baseline for Platelet count: is defined as the average of all available measurements, including central lab measurements and local lab measurements, prior to Day 1 of volanesorsen, i.e.

1. For subjects in Group 1 and 2 who were treated with volanesorsen in the index study, it is all available measurements prior to Day 1 of treatment in index study
2. For subjects in Group 3, it is all available measurements prior to Day 1 of treatment in this Open-label study

3. For subjects in Group 1 and 2 who were treated as placebo in the index study, it is all available measurements within 4 weeks prior to Day 1 of volanesorsen in this open-label study.

Safety Baselines for 12-lead ECG: is defined as the average of the triplicate ECGs taken on screening visit of this Open-label study or the last visit in the parent study, if only one or two assessments are available, the single assessment or average of the two assessments will be used.

4. For subjects in Group 1 and 2 who were treated as volanesorsen in the index study, it is the last visit prior to Day 1 of treatment in index study
5. For subjects in Group 3 and subjects in Group 1 and 2 who were treated as placebo in the index study, it is the last visit prior to Day 1 of treatment in this Open-label study

Safety Baselines for vital sign, clinical safety lab (except for the platelet) and MRI

It is defined as last non-missing assessment prior to Study Day 1 pre-dose of volanesorsen in index studies or Open-label study.

Safety Baselines for MRI: is defined as last non-missing assessment on or prior to Study Day 14 of volanesorsen in index studies or Open-label study.

Baselines for analyses:

- Efficacy analyses are based on the **Index study Baseline** and the **Open-label study Baseline**. Details of separate analyses based on each baseline will be specified in the [section 3.3](#).
- Safety analyses are based on **Safety Baseline**. Details of separate analyses based on each baseline will be specified in the [section 3.5](#).

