For patients in the PK subgroup only, non-compartmental PK analysis of volanesorsen will be carried out on each individual patient data set using data collected in the open-label study from the intensive PK subgroup, following a single dose (i.e., single-dose PK) or multiple doses (i.e., steady-state PK), depending on their earlier treatment in the index studies (Group 1 and Group 2 Patient). On Week 1 Day 1 of the open-label study, patients who received placebo in the index study (and all patients in Group3) will receive the first treatment of volanesorsen (single-dose PK), while patients who received volanesorsen in the index studies had been on volanesorsen treatment for 12 months (ISIS 304801-CS6) or 6 months (ISIS 304801-CS16), thus the PK data collected from these patients reflect steady-state PK. The maximum observed drug concentration (C_{\max}) and the time taken to reach C_{\max} (T_{\max}) will be obtained directly from the concentration-time data. Area under the plasma concentration-time curve from time zero to 24 hours (AUC_{0-24h}) will be calculated using the linear trapezoidal rule. Apparent systemic (plasma) clearance after SC administration (CL_{0-24h}/F) will be calculated from $CL_{0-24h}/F = \text{Actual Dose}/AUC_{0-24h}$. Mean residence time (MRT) from time zero to 24 hours after the SC administration will be calculated from the equation, $MRT_{0-24h} = AUMC_{0-24h}/AUC_{0-24h}$, where $AUMC_{0-24h}$ is the area under the moment plasma concentration-time curve from time zero to 24 hours after the SC administration. Other PK parameters, as appropriate, may be determined or calculated at the discretion of the PK scientist.

Plasma PK parameters will be summarized using descriptive statistics for 2 groups (Treatment naive group and CS6-Volanesorsen and CS16-Volanesorsen Combined), with and without stratification by IM status.

Population PK, PK/PD, and covariate analysis may be performed if deemed appropriate, and results will be reported separately. This SAP do not include relevant analysis plan.

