3.5.6 Physical Examination

Adverse changes in physical examinations that are deemed clinically significant by the investigator will be classified as AEs. Physical examination results will be listed.

3.5.7 12-Lead Electrocardiogram

ECGs will be performed in triplicate at the visits indicated in the protocol Schedule of Procedures. The ECG data will include ventricular rate, PR interval, QRS duration, QT and corrected QT intervals, and Overall interpretation. For the continuous variables, the average of measurements at a given visit will be used for analysis. For overall interpretation, the worst categorical results of triplicate results and the associated findings will be used for analysis. For the continuous variables above, descriptive statistics (n, mean, standard error, standard deviation, median, 25th percentile, 75th percentile, minimum, and maximum) of the results, as well as the change from baseline to each study visit, will be presented by the group presented in [Section 3.2.1](#) including overall in summary tables; for the categorical responses to overall interpretation, counts and percentages will be provided.

All the data collected in triplicate will be listed.

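### The opening sentence of the ECG safety baseline contradicts item 4 for patients who took volanesorsen in the index study; applied to them, it would drop ECG change that arose during that study

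*SAP*

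**What the plan says.** SAP section 3.2.3 defines the 12-lead ECG safety baseline in two layers.

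- The opening sentence, which applies to everyone as worded, averages triplicate ECGs "taken on screening visit of this Open-label study or the last visit in the parent study". It adds that one or two readings suffice if three are not available.
- Two numbered items follow (4 and 5; the numbering runs on from the platelet list). Item 4 covers Group 1 and 2 patients who received volanesorsen in the index study: "it is the last visit prior to Day 1 of treatment in index study". Item 5 covers Group 3 and the index-placebo patients: "it is the last visit prior to Day 1 of treatment in this Open-label study".

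The baseline is used in section 3.5.7, which summarises the continuous ECG variables (ventricular rate, PR, QRS, QT and corrected QT) at each visit, "as well as the change from baseline to each study visit", by group and overall. Section 3.5 restricts what the tables show: "Visits of summary tables include baseline and labeled post baseline visits in the open-label study". ECG results are a listed safety endpoint in section 1.4.2.

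**The concern.** For an index-volanesorsen patient, the opening sentence and item 4 cannot both be followed. Both visits named in the opening sentence fall after months of treatment, whereas item 4 goes back to before the first index-study dose.

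At stake is the reference point for a cardiac safety summary. An ECG taken on drug already contains whatever the drug did during the index study. Measuring change from it subtracts that effect out of the CS6-Volanesorsen and CS16-Volanesorsen columns. It also leaves the Overall column averaging changes from two different kinds of baseline.

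**Working it through.** The SAP gives no ECG figure to reproduce, so the check is a comparison of texts followed by simple algebra.

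**Step 1: which ECG each rule selects.** Section 3.4.1.2 puts index-volanesorsen patients on drug for 12 months (CS6) or 6 months (CS16) by open-label Day 1. Section 2.1.1 gives Groups 1 and 2 a qualification period of up to 2 weeks after the index study, unless the sponsor approves otherwise. Screening belongs to Group 3.

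| Patients | Opening sentence | Items 4 and 5 | Same kind of baseline? |
|---|---|---|---|
| Volanesorsen in CS6 or CS16 | Last parent-study visit (or a visit at open-label entry): on drug | Item 4, before index Day 1: pre-drug | No |
| Placebo in CS6 or CS16 | Last parent-study visit: pre-drug | Item 5, before open-label Day 1: pre-drug | Yes |
| Group 3 | Open-label screening: pre-drug | Item 5, before open-label Day 1: pre-drug | Yes |

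The opening sentence suits the item 5 patients. None of its options can satisfy item 4.

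**Step 2: what the rest of the SAP implies.** Section 3.5 says of patients on active index treatment that "Day 1 of Volanesorsen will be the first day volanesorsen is administered in the index study". The baseline for vital signs and safety laboratory tests (platelets apart) is also pre-drug: "It is defined as last non-missing assessment prior to Study Day 1 pre-dose of volanesorsen in index studies or Open-label study". The platelet baseline in 3.2.3 has the same layout as the ECG one, but its opening sentence is anchored to the first volanesorsen day and agrees with its group items. Among these, only the ECG opening sentence departs from the pattern.

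**Step 3: effect on a patient's reported change.** Let B be the ECG value before the index study, d1 the change during the index study and d2 the further change up to a given open-label visit. The value at that visit is B + d1 + d2.

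- Item 4 baseline: (B + d1 + d2) − B = d1 + d2.
- Last parent-study visit as baseline: (B + d1 + d2) − (B + d1) = d2.
- Difference: d1.

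**Step 4: effect on the Overall mean.** Let f be the share of index-volanesorsen patients at the visit, d1 and d2 now their mean changes, and n the mean change in the treatment-naive group.

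- Item 4: (1 − f) × n + f × (d1 + d2).
- Opening sentence: (1 − f) × n + f × d2.
- Difference: f × d1.

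The SAP does not give f. For an assumed f of 0.25 to 0.5, the Overall mean would be short by 0.25 × d1 to 0.5 × d1. In the special case of a constant shift d that is complete by the end of the index study and equally large in the naive group (d1 = d, d2 = 0, n = d), the index-volanesorsen columns would read 0. Overall would then read (1 − f) × d, which is 0.75d to 0.5d over the same assumed range.

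**Step 5: whether d1 could be recovered elsewhere.** Under the opening sentence the baseline row would itself show B + d1. Section 3.5 limits the ECG tables to baseline and open-label visits, and the patient listings to data collected in the open-label study. As that section describes the output, B would not appear for these patients and d1 could not be read off.

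**The case against.** The strongest reply is that items 4 and 5 settle the matter. They stand directly under the opening sentence, they are specific to group, and between them they place every patient in exactly one rule. The opening sentence can be taken as supplying the averaging rule, with the items fixing the visit. The definition of Day 1 of Volanesorsen and the other safety baselines agree. An analyst reading the specific rule over the general one would arrive at item 4. This stands, and it means the plan did not choose an on-drug baseline. A reader might infer that the SAP leaves two rules of equal standing with nothing to decide between them, but the context does not support that.

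A reader might also infer that the on-drug baseline would hide any ECG change whatever the drug does. Step 3 shows otherwise: only d1 is lost and d2 still shows. A reported change near zero needs an effect complete by the end of the index study and steady afterwards, and nothing in the SAP establishes that.

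Finally, the ECG output is descriptive, section 1.3 states no formal hypothesis, and measured values are tabulated beside changes. The treatment-naive column has a pre-drug baseline under either rule. All of this limits the consequence. The tabulated values do not repair it, though, because the pre-drug value would be missing from the tables if the opening sentence were used.

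The objection does not remove the contradiction. The opening sentence names specific visits, is not restricted to item 5 patients, and conflicts with item 4 for a defined group.

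**Conclusion.** The definition is wrong as written, at low severity. For patients treated with volanesorsen in CS6 or CS16, the opening sentence contradicts item 4, and the SAP as a whole favours item 4.

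The consequence depends on the opening sentence being the rule that is programmed. In that case the change-from-baseline summaries for ventricular rate, PR, QRS, QT and corrected QT would be off by d1 in the CS6-Volanesorsen and CS16-Volanesorsen columns and by f × d1 in Overall, and Overall would mix on-drug and pre-drug baselines. No figure in milliseconds can be given, because the SAP states neither d1 nor f. If item 4 is programmed, nothing is lost. Group 3 and index-placebo patients keep a pre-drug baseline either way.

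**What to change.** Delete the visit clause from the opening sentence, or limit it expressly to item 5 patients. Define the ECG safety baseline as the average of the available triplicate ECGs at the last visit before Day 1 of Volanesorsen, with a cross-reference to section 3.5, where that term is defined. Keep the allowance for one or two readings, and keep items 4 and 5 as they are.

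The cost is one edited clause. No new data or analysis is needed, since item 4 already calls for the pre-index ECGs. If ECG tables have already been programmed, check that the baseline for index-volanesorsen patients was taken before index Day 1.
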